## A. Introduction and Background

It is well documented that children exposed to parental drug use are at greater risk for maladjustment, deviant peer affiliation, and substance use initiation. Parents living with Opioid Use Disorder (OUD) are at high risk for incarceration, family disruptions, health problems, and financial hardship. However, research on drug abuse with men has largely neglected the role of fathering, parenting roles and parenting status for these men. Moreover, our understanding of the unique impacts of opioid misuse on fathering behaviors is even more limited than our knowledge base for mothers. The majority of extant research has been conducted on mothers, although there is evidence that more fathers than mothers enter into drug abuse treatment.

Existing opioid research suggests there are marked parenting differences for fathers and mothers who misuse opioids. Compared to mothers, fathers are more likely to be misusing opioids when they first become a parent, and compared to fathers without a substance use disorder, fathers with OUD exhibit more concerning parenting behaviors and report other limitations that may impact their children. For parenting specifically, compared to fathers without OUD, OUD fathers report lower parental efficacy, engage in fewer positive parenting behaviors such as consistency and positive involvement, and report less satisfaction with the parenting role compared to mothers. Fathers who misuse opioids also report greater prevalence of violence towards their child's mother both over the course of the relationship and report greater violence perpetrated against them by their child's mother.

Within the preventive intervention and treatment research, fathers are vastly underrepresented in studies of parent training relative to mothers, with only a handful of studies including father-related outcomes. Less is known about fathers who do or do not misuse opioids, or what mechanisms are unique to opioid use that interfere with effective parenting. The goal of this pilot is to better understand the unique, specific, influence of opioid misuse on compromised fathering behaviors, and further, how misuse uniquely affects the process of intervention uptake. We will use Fathering Through Change, an evidence-based parenting intervention which has been found to be efficacious for positive changes in fathering mediated by changes in parent efficacy and fathering identity.

## B. Specific Aims/Study Objectives

Aim 1: Document Baseline Differences Among Opioid Misusing and Non-Opioid Using (other substance using) Fathers and Child Functioning (note, we are recruiting from substance use treatment centers and substance use related pages on social media so some fathers use opioids while others do not just by nature of who attends treatment)

Aim 2: Understand how Opioid Misuse is related to treatment outcomes and whether the intervention shows promise for this population

## C. Methods, Materials and Analysis

This study will include two procedures; Procedure 1 is for the intervention study and Procedure 2 is for the baseline study.

Procedure 1 for the intervention study is a randomized-control trial of the Fathering Through Change (FTC) intervention. Our goal is to recruit up to 120 participants and randomly assign them to either intervention or control. Treatment centers throughout the state of Oregon will help to facilitate recruitment. They will do outreach to men currently receiving treatment services and to men who have received treatment from the respective treatment centers in the past. Individuals who receive communication from a treatment center may also share that information with their peers in recovery. Those individuals will also be welcome to participate if they meet the inclusion/exclusion criteria. The clinician does not have to be vetted by in order to provide services for men currently receiving treatment since they are not an employee of any treatment center and have been vetted by the University of Oregon. Additionally, the study will recruit participants by advertising on social media websites, specifically Facebook and Reddit. Public account pages will be made on each platform to advertise the current study. The recruitment flyer and posted text (see "Fathering Through Change (FTC) Intervention Research Study.pdf" and "Facebook or reddit example posting.docx" will be posted on both platforms. For Facebook, the flyer and posted text will be posted to groups related to heroin/opioid/substance use recovery and parenting. For Reddit, a similar process will occur, such that the flyer and posted text will be posted to "communities" that relate to heroin/opioid/substance use recovery and parenting in recovery. In addition to the flyer and posted text, contact information will be shared that can connect interested individuals with affiliated research personnel. All individuals expressing interest in the study will be directed to contact the project coordinator to complete the eligibility screener.

All eligible and consented participants for Procedure 1 will be invited to take three sets of surveys using Qualtrics or RedCap. IP address tracking will be enabled for all surveys in effort to increase security measures and reduce fraudulent survey submissions. First at baseline (pre); second, at 6-weeks later (post); and lastly, at 4 months from baseline (follow-up). Surveys will be conducted online on the participants electronic device and will be formatted for administration on a computer, tablet, or smartphone. Surveys will assess the parent-child relationship, child behavior, parent mental health, parent substance use, intervention knowledge gained and satisfaction, and participant context. The baseline questionnaire will take approximately 95 minutes. The post questionnaire will take approximately 90 minutes. The follow-up questionnaire will take approximate 90 minutes.

These are the steps for participation:

1. Treatment center sends out text messages and emails to current and past male clients. They will not send out text messages and emails to current in-patient clients because these clients do not have access reliable access to technology (not allowed to use it). The text message will contain information to contact the study team. Formal recruitment will occur when the potential participant reaches out to the study team via phone or email. For Facebook and Reddit recruitment, the project coordinator will post the recruitment flyer to groups and communities on both platforms. All interested individuals will contact the project coordinator and complete the formal recruitment process including the eligibility screener.

See **Text Messages** document.

2. For both Procedure 1 and Procedure 2, the study team will respond to interested participants with an enrollment text from a google voice number or study specific email. They will first ask screening questions to determine eligibility. If a participant is eligible, they will provide a link to the electronic survey.

See **Text Messages** document.

3. The first page of the survey will take participants to a screener to ensure they are eligible to participate. We will screen for past 18 month (Procedure 1) and 36 month (Procedure 2) abstinence from illicit substance use (For Procedure 1, must have less than an 18 months of abstinence from illicit substances. For Procedure 2, must have less than a 36 months of abstinence from illicit substances), child in appropriate age range and at least two hours per week spent with child. Regarding Procedures 1 and 2, participants who are ineligible will be taken to the end of the survey and will not receive follow-up. Participants who are eligible will complete the informed consent process electronically. After consenting, they will take the baseline questionnaire survey. In the baseline survey, we will include a questionnaire related to the psychological and parenting consequences of COVID-19 (see "Measures Overview\_8\_31\_20.docx") to better understand the impacts of COVID-19 on fathers' parenting, ability to care for their child(ren), distress, and potential substance use cravings and use.

4. For both Procedures 1 and 2, during the survey, they will provide their contact information so that they can receive either an electronic gift card or check in the mail, depending on their preference as an incentive. This information will also be used to provide them with study materials, reach out for follow-up surveys (Procedure 1), and link participant data overtime (Procedure 1).

5. For Procedure 1, once they have completed the questionnaire, they will receive a follow-up text message and email (at least one method depending on information given) within one week to welcome them to the study. Different messages will be provided depending on whether a participant is assigned to the control or intervention group. Random assignment will occur using a random number generator in batches of 10 (up to 100 pre-determined for eligible participants- assigned at the time of enrollment) to ensure the design is balanced if our sample size is smaller than expected.

6. For Procedure 1, the PI will provide videos to the participant on a weekly basis for 6 weeks. The participant will have the opportunity to take a brief knowledge test after watching each video to earn an additional \$5 per knowledge test completed. The PI will schedule appointment for the coach to call via text or email with participants.

See **Text Messages** document.

7. For Procedure 1, the clinician will call participants at the designated appointment time using a google voice number at week 1, week 3, and week 5. Since these are just opportunities to check-in, if a participant misses their appointment, they will have the opportunity to check-in again. However, this will be the participants responsibility- the PI will not make another attempt to schedule a coaching call. If the participant asks to check-in via text instead, the clinician may also use the google voice number to check-in via text using the same script. Please note that the coaching calls document is a loose script and may be adapted by the clinician. The clinician is responsible for providing notes after each call, but calls will not be recorded.

See **Coaching Calls** document.

8. See **Text Message** document for a full overview of when participants will be contacted for each component of the study and what content will be provided.

Procedure 1:

Control (approx. 40 fathers)	Intervention Condition (approx. 40 fathers)
Services as Usual:	All Services as Usual PLUS

Current or previous substance use disorder treatment Medication Assisted Treatment (if applicable) Some Parenting Coaching if still in treatment
	
Fathering Through Change Intervention: 6 weekly video clips, texted to their phone, approximately 5-15 minutes per week with a follow-up knowledge quiz (see Text Message document) Opportunities for three 20 minute check-ins with a clinician ([name]) who is not affiliated with any treatment center Will receive a certificate of completion

---	---

Procedure 2 for recruiting participants only for the baseline survey:

For Procedure 2 interested individuals will text or email "I'm Interested" to the study phone number or email. The project coordinator will complete the eligibility screener and, if eligible to participate, send the eligible individual the link to the Qualtrics survey. If eligible to participate, the survey will continue to inform the eligible individual to review the consent form (see "Informed Consent\_Baseline only\_A6.docx"). Once consent is completed, the participant will complete the baseline survey that includes the same questionnaires from the previously approved baseline survey of the intervention study. Participants will have the opportunity at the end of the Qualtrics survey to indicate if they consent to be re-contacted for future research studies; in effort to potentially enroll them in the intervention study (Procedure 1). Participants will be compensated \$50 for completing the baseline survey.

Procedure 2 will recruit participants through both social media and treatment center outreach. Treatment centers previously contacted for Procedure 1 will be contacted via email (see "email template for treatment centers\_baseline.docx") to send them a flyer (see "Baseline only FTC flyer.pdf"). For social media, we will recruit participants by advertising on social media websites, specifically Facebook and Reddit. Public account pages will be made on each platform to advertise the current study. The recruitment flyer and posted text (see "baseline only FTC flyer.pdf" and social media template\_baseline.docx") will be posted on both platforms. For Facebook, the flyer and posted text will be posted to groups related to heroin/opioid/substance use recovery and parenting. For Reddit, a similar process will occur, such that the flyer and posted text will be posted to "communities" that relate to heroin/opioid/substance use recovery and parenting in recovery.

In effort to reduce fraudulent survey submissions anticipated from posting our study on social media platforms, three actions will be taken: 1) we will remove the compensation option "giftcard by text" and prompt "if receiving mail is a problem for you check this box" followed by the option to indicate, "I don't have a mailing address. Please follow-up with me", 2) implement IP address restrictions on the Qualtrics survey settings, and 3) add three fill in the blank attention checks to assess for fraudulent and bot responses (see "example attention check questions.docx").

**Analysis Plan** The research does not involve any procedures typically used in a biomedical/clinical setting and/or administration of medications. To address aims, we will use quantitative analyses including, *t*-tests, 2 x 2 ANCOVAs and MANOVAs, for test of mediation and moderation we will specify structural equation path models. Identifiable information will be collected but data will be reported anonymously. Research will be disseminated at conferences and through scientific journals, and press releases. Findings will also be shared through outlets deemed appropriate by the larger center this study is a part of (noted in the funding and sponsorship form).

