#### **D. Research Population & Recruitment Methods**

**Procedure 1 (Intervention Study):** The participant population are fathers who are in recovery from substance use disorders and have been abstinent from illicit substances for less than 18 months. Participants must be over the age of 18 years old. Our primary intervention target is fathers with opioid use disorder and efforts will be made to prioritize fathers who have specifically misused opioids in the past.

Fathers are eligible to participate if:

1. They identify as being in recovery and have been abstinent from illicit substances for at least 1 day and less than 18 months.
2. They have parenting responsibilities for a child between the ages of 3-16 who they spend at least 2 hours per week with.
3. They speak English.
4. They are 18 and older.

The project coordinator will complete the eligibility screener via text message or phone call. Individuals will be asked to describe their recovery and family situation to the project coordinator through open ended questions. Individuals will be excluded if they do not meet eligibility criteria, or if they deny answering questions about their recovery and family situation. Individuals will be excluded if they cannot speak English because they will not be able to understand intervention content and will not be able to participate in surveys. Father's must have potential to have some contact following treatment since the intervention is targeted at improving parenting skills. Fathers of children younger than 3 or older than 16 will be excluded because the intervention is not suitable for children outside of the age range 3-16.

The total number of participants will not exceed 80 for procedure 1. Our goal is to recruit approximately 40 fathers to the intervention condition and 40 fathers to the control condition. This will provide enough data to compare effectiveness between condition and also to examine the effects of different substances on intervention outcomes. We expect these numbers may be less due to COVID-19.

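### The Protocol gives two maximum sizes for the randomised study, 120 in Section C and 80 in Section D, and Section G does not say which applies to Procedure 1.

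*Protocol*

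**What the plan says.** Protocol Section C defines Procedure 1 as the randomised trial of the intervention and gives its size as follows: "Our goal is to recruit up to 120 participants and randomly assign them to either intervention or control".

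Other places bear on the same number:

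- **Section D, Procedure 1:** "The total number of participants will not exceed 80 for procedure 1", followed by "Our goal is to recruit approximately 40 fathers to the intervention condition and 40 fathers to the control condition".
- **Section C, Procedure 1 arm table:** about 40 fathers in each column; the control column reads "Control (approx. 40 fathers".
- **Section C, step 5:** random assignment is made "in batches of 10 (up to 100 pre-determined for eligible participants- assigned at the time of enrollment", with the stated purpose "to ensure the design is balanced if our sample size is smaller than expected".
- **Section D, Procedure 2:** the baseline survey is capped at 120, and that cap counts the fathers already in Procedure 1. The text anticipates that Procedure 1 recruitment is finished with 41 enrolled, which leaves at most 79 for the baseline-only survey.
- **Section G:** in a list of differences from the Data Safety Monitoring Plan sent to the funder, the sample size is said to be 120 where it had been 80. No procedure is named. The differences are said to be recorded in a Memo to File, which is not among the documents.

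On what the planned size can show, Section D says of 40 + 40: "This will provide enough data to compare effectiveness between condition and also to examine the effects of different substances on intervention outcomes". The next sentence is "We expect these numbers may be less due to COVID-19". The SAP calls the sample small and gives no number, power or precision.

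**The concern.** A randomised trial should have one planned maximum. Section C sets a goal for randomised fathers that is 40 higher than the cap in Section D. Because Section C says that the 120 are assigned to intervention or control, it cannot be read as including baseline-only fathers, who are not randomised. One of the two sections is therefore wrong as written. Section G could have settled the question but does not say what its 120 refers to.

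What is at stake is how the trial is read against its plan. Someone reporting or appraising it needs to say how far enrolment fell short, and the answer depends on which section is used. The only statement about what the sample can show is tied to 40 per arm, so a reader also needs to know that it does not describe the number enrolled.

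**Working it through.** **1. The sizes side by side.**

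| Place | Figure | What it describes |
|---|---|---|
| Section C, opening of Procedure 1 | 120 | fathers recruited and randomised |
| Section C, arm table | about 40 + 40 = 80 | fathers per arm |
| Section D, Procedure 1 | 80; about 40 + 40 | cap and per-arm goal |
| Section D, Procedure 2 | 120 | baseline survey, counting Procedure 1 fathers |
| Section G | 120 in place of 80 | not stated |

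The difference between the two Procedure 1 figures is 120 - 80 = 40, or 40/80 = 50% of the cap.

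**2. Where 120 probably comes from.** The Procedure 2 text subtracts the Procedure 1 enrolment from 120: 120 - 41 = 79, which reproduces the stated figure. There, 120 is a total over both procedures. This fits a Procedure 1 cap of 80 and suggests that Section C carries the combined total. It does not prove it: a Procedure 1 maximum of 120 would also respect the combined cap, leaving 120 - 120 = 0 for the baseline-only survey.

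**3. The assignment list.** In batches of 10, a list of up to 100 is 10 batches. A maximum of 80 needs 8 and is covered. A maximum of 120 needs 12, so the list would be 120 - 100 = 20 assignments short.

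**4. Shortfall under each maximum.** 41/80 = 0.5125, or 51%. 41/120 = 0.342, or 34%.

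**5. Precision at 41 against 80.** The documents give no significance level, power, effect size, standard deviation, dropout or actual split, so the 40 + 40 figure can be neither reproduced nor refuted. The relative width of the interval needs fewer inputs. Assume a two-sided 95% interval, a 21/20 split and no attrition. The half-width is t × f × sqrt(1/n1 + 1/n2), where f is the residual standard deviation and is taken to be the same at both sizes, so it cancels in the ratio.

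- Standard error ratio: sqrt[(1/21 + 1/20)/(1/40 + 1/40)] = sqrt(0.09762/0.05) = 1.397.
- t quantiles with one baseline covariate (df = N - 3): 2.024 at N = 41 and 1.991 at N = 80, ratio 1.017.
- Width ratio: 1.397 × 1.017 = 1.42.

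A 25/16 split gives 1.46. Equal 20% attrition (17/16 against 32/32) gives 1.42. The interval is thus about 1.4 times as wide, which is little more than the square root of the ratio of sample sizes, sqrt(80/41) = 1.40.

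**The case against.** The best defence is that the conflict is close to clerical. The Procedure 2 text shows where 120 arises, two places give about 40 per arm, and recruitment is anticipated to be finished at 41, under either ceiling. No participant, analysis or result changes. All of this stands, and it makes the point minor. It does not remove the contradiction: Section C still says that 120 are randomised, and the section that might explain the change names no procedure.

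Three stronger readings are tempting, and the documents do not support them.

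- *A reader might take 100 as a third planned size.* It is the length of a list of pre-determined assignments. A list longer than the cap is compatible with a cap of 80. It matters only if 120 is confirmed.
- *A reader might say that the 41 enrolled contradict the statement about enough data.* That statement is qualitative, refers to 40 + 40, and is followed at once by a warning that numbers may be lower. Step 5 of Section C plans for a smaller sample, the SAP calls the sample small, Section A calls the study a pilot, and Aim 2 asks whether the intervention shows promise. A statement about a target does not become false when the target is missed.
- *A reader might conclude that the trial is adequately powered at 80, or underpowered at 41.* Neither follows. For an effect of 0.5 SD (two-sided 5%, baseline-adjusted mean of two follow-ups, assumed baseline-to-follow-up correlation 0.4 to 0.7 and between-wave correlation 0.5 to 0.7), power runs from 76% to 99% at 40/40 and from 47% to 86% at 21/20. All these inputs are assumptions, and the calculation leaves out the false discovery rate correction over five primary outcomes.

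It is also fair to say that 41 may not be final. The text only anticipates that recruitment is finished, and Section C allows Procedure 2 fathers who agree to re-contact to be considered for Procedure 1. The figure is the enrolment when that text was written, not a final or randomised count.

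**Conclusion.** The Protocol contradicts itself on the maximum for Procedure 1: 120 randomised in Section C, 80 in Section D. The weight of the text favours 80, with 120 as the total over both procedures, but the documents do not settle it. The practical size of the problem is the reading of enrolment: 51% of plan or 34% of plan. The conflict itself rests on the text alone and needs no assumption.

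The secondary point is smaller. The statement about enough data covers 40 + 40 and nothing else. At 41 fathers the interval for the condition comparison would be about 1.4 times as wide as at 80, assuming a near-equal split and the same residual variation. This is a reason to show the interval, not a finding that the sample size was miscalculated. Nor is it a reason to relabel the substance-related question as exploratory, since Aim 2 itself names opioid misuse and treatment outcomes.

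Severity is minor, because recruitment is anticipated to be finished below either maximum.

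**What to change.** 1. The sponsor confirms the Procedure 1 maximum against the Memo to File cited in Section G, and aligns Sections C, D and G.
2. If 80 is confirmed, the opening of Procedure 1 in Section C changes to 80, and Section G states that 120 is the combined total of both procedures.
3. If 120 is confirmed, the arm table in Section C and the cap and per-arm goal in Section D change, and the assignment list in step 5 is extended from 100 to cover 120.
4. The condition comparison is reported with observed confidence intervals and described as a pilot estimate.

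The cost is a few changes of wording and the reporting of intervals that the fitted models already supply. The downside, if 80 is confirmed, is that the stated planned size of the randomised study becomes smaller. No change to enrolment or data is proposed.
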